5.1.1 Phase I Study Drug Administration

- The eligible subjects will begin standard of care dosing of enzalutamide at 160mg/day.
- Beginning day 29, subjects will enter phase I combination drug portion of the study beginning at mifepristone dose 0 and at enzalutamide dose A (40mg/day). Dose levels are defined in Table 1.
- After the first 6 patients are evaluated at this dose level, subsequent patients will be enrolled and dosed similarly (after 28 day standard dose lead in) with dose of enzalutamide and mifepristone to be determined based on the following dose escalation/de-escalation rules.

5.1.1.1 Phase I Dose Level Determination

Mifepristone and enzalutamide dose levels (Table 1) will be adjusted by dose cohorts according to the following rules, which are illustrated in the algorithm below (Figure 3). Each cohort will enroll a minimum of six patients, beginning with dose level 0A, with additional patients added or doses adjusted as described in the algorithm by following rules 1-4 in order to take into account dose limiting toxicity (DLT) rate and the change in steady-state (C_{trough}) enzalutamide levels (†, Figure 3). As noted above, it is estimated that mifepristone at both 300mg and 600mg will increase enzalutamide exposure by approximately 4-fold, with no significant difference in CYP inhibition based on mifepristone

dose. Thus, the initial dose level for enzalutamide, to ensure safety is $\frac{1}{4}$ the standard dose of 160mg/day. As noted in the Figure 3 rules, if enzalutamide plasma levels are lower then expected, the enzalutamide dose will be increased for the next cohort (e.g. from A to A'), whereas if higher then anticipated, the dose will be decreased (e.g. from A to B).

[figure not shown]
Mifepristone dose will be escalated or decreased based on tolerability (DLT rate-see proceeding section). **The recommended Phase II dose (RP2D) will be the highest mifepristone dose in combination with enzalutamide such that <33% (4/12) experience DLT and $\checkmark \leq 1.5$.** Although we anticipate that a 12 patient cohort will be sufficient to estimate effect of mifepristone on enzalutamide clearance and that the intra-patient comparison will account for variability within each patient in baseline enzalutamide clearance characteristics, it is possible that the variability in affect of mifepristone on enzalutamide metabolism will be larger then anticipated. In this case, dose cohorts will be expanded in a protocol amendment to better characterize PK interactions.

Table 1. Dose levels

Mifepristone		Enzalutamide	
Level	Dose	Level	Dose
-1	300 mg/every other day	A'	80 mg/day
0	300 mg/day	A	40 mg/ day
1	600 mg/day	B	40 mg every other day
		C	40 mg every 3 rd day

[Rest of Page Intentionally Left Blank for Formatting Purposes]

Figure 3. Phase I schema and dose escalation/de-escalation algorithm

r_i = ratio of trough drug concentration after 28 days concurrent dosing divided by trough drug concentration after 28 days enzalutamide alone dosing for an individual patient

$= [C_{trough} \text{ Enzalutamide} + C_{trough} \text{ M2 metabolite}] \text{ day 57} / [C_{trough} \text{ Enzalutamide} + C_{trough} \text{ M2 metabolite}] \text{ day 29}$

\bar{r} = average of r_i for all patients within a dose cohort (i.e., mean of 6 or 12 patients)

[figure not shown]
5.2 Dose Limiting Toxicity Definition

A grade 3 or 4 toxicity (CTCAE 4.0, <http://evs.nci.nih.gov/ftp1/CTCAE/About.html>) that is potentially related to the therapy will be classified as a dose limiting toxicity (DLT). There will be a 28day DLT monitoring period (after combination treatment) during the phase I study in which safety will be examined prior to dose escalation from 300mg to 600mg. A 28 day DLT period was chosen as the majority of dose limiting toxicities seen with enzalutamide, including rare seizures were seen in this period in previous phase I/II studies were seen within 6 weeks of beginning enzalutamide and patients will be on enzalutamide for 28 days prior to combination dosing already¹⁵. The DLT period begins at day 29, upon the onset of concurrent mifepristone and enzalutamide drug daily administration, and ends at day 57, four weeks later.

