10.5 Serious Adverse Event Reporting

This study will be using MedWatch for SAE reporting.

MedWatch forms and information: <http://www.fda.gov/medwatch/getforms.htm>

The minimum information required for SAE reporting includes identity of investigator, site number, patient number, an event description, SAE term(s), onset date, the reason why the event is considered to be serious (ie the seriousness criteria) and the investigator's assessment of the relationship of the event to study treatment. Additional SAE information including medications or other therapeutic measures used to treat the event, action taken with the study treatment due to the event, and the outcome/resolution of the event will be recorded on the SAE form.

In all cases, the investigator should continue to monitor the clinical situation and report all material facts relating to the progression or outcome of the SAE.

When reporting serious adverse events, the following additional points should be noted:

- When the diagnosis of an SAE is known or suspected, the investigator should report the diagnosis or syndrome as the primary SAE term, rather than as signs or symptoms. Signs and symptoms may then be described in the event description.
- Death should not be reported as an SAE, but as an *outcome* of a specific SAE, unless the event preceding the death is unknown. In the exceptional case where the events leading to death are unknown, then Death may be used as an event term and should be reported as "death, cause unknown". If an autopsy was performed, the autopsy report should be provided.
- While most hospitalizations necessitate reporting of an SAE, some hospitalizations do not require SAE reporting, as follows:
 - Elective or previously scheduled surgery, e.g., a previously scheduled ventral hernia repair.
 - Procedures for pre-existing conditions that have not worsened after initiation of treatment.
 - Pre-specified study hospitalizations for observation.
 - Events that result in hospital stays of less than 24 hours and that do not require admission, eg, an emergency room visit for hematuria that results in a diagnosis of cystitis and discharge to home on oral antibiotics.

- SAEs must, however, be reported for any surgical or procedural complication resulting in prolongation of the hospitalization.
- Symptoms related to progressive diseases uc has severe bone pain will not be reported as toxicity or as Serious Adverse Events.

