10.8.5 Independent Safety Monitor

[name], PhD, Director for Clinical Research Operations in the University of Chicago Comprehensive Cancer Center, will serve as the Independent Research Monitor (IRM) for this study as stipulated by DOD Directive 3216.02. The principle role of the IRM within the context of this study will be to oversee study conduct specifically with respect to safety. Given the phase I/II nature of the study, and the potential for dose adjustments based on both pharmacokinetics and safety, the IRM will have direct oversight with respect to assessment of patient safety, independent of the research team. In the case of serious adverse events or subject deaths that she feels meet the criteria to be classified as unanticipated problems, her independent report in the form of a memo will be promptly submitted to the DOD (USAMRMC ORP HRPO) and University of Chicago IRB along with the report of the event. In addition to attending weekly data safety monitoring meetings, she will participate in the regular teleconferences once more than one site is participating in the trial. In the event that she is not able to attend the data safety monitoring meeting in person, she will review the data safety monitoring minutes from that meeting. Specifically, she will review all unanticipated problems involving risk to subjects or others, serious adverse events and all subject deaths associated with the protocol and provide an unbiased written report of the event should she feel it qualifies as an unanticipated problem. For those events qualifying as unanticipated problems, the IRM will comment on the outcomes of the event or problem and, in case of a serious adverse event or death, she will comment on the relationship to participation in the study. The IRM will indicate whether she concurs with the details of the unanticipated problem report provided by the principal investigator. Reports for events determined by either the investigator or research monitor to be possibly or definitely related to participation and reports of events resulting in death will be promptly forwarded to the USAMRMC ORP HRPO and the University of Chicago IRB. The IRM has the authority to stop this research protocol in progress in parallel with the submission of a UP to the University of Chicago IRB, remove individual human subjects from this research protocol, and take whatever steps are necessary to protect the safety and well-being of human subjects participating in this protocol until the University of Chicago IRB assesses the UP and the IRM's report and determines appropriate next steps.

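### The DLT definition in Section 5.2 stops at grade 4, so read literally a related death with no earlier grade 3–4 record is left out of the count that sets the dose

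*Combined protocol and SAP*

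**What the plan says.** Section 5.2 holds the only DLT definition in the readable text: "A grade 3 or 4 toxicity" under CTCAE 4.0, potentially related to therapy. On timing it says: "The DLT period begins at day 29, upon the onset of concurrent mifepristone and enzalutamide drug daily administration, and ends at day 57". It calls this a monitoring period "in which safety will be examined prior to dose escalation from 300mg to 600mg".

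Section 5.1.1.1 puts the count to use. Mifepristone goes up or down according to the DLT rate, and the recommended phase II dose is the highest mifepristone dose at which "<33% (4/12) experience DLT", together with a limit on the enzalutamide trough ratio.

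Two other sections deal with deaths:

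- Section 10.5, on reporting, states "Death should not be reported as an SAE, but as an" outcome of a specific SAE. Where the preceding events are unknown, it allows death of unknown cause as an event term.
- Section 10.8.5 has the independent research monitor review all deaths and adds: "The IRM has the authority to stop this research protocol in progress".

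**The concern.** CTCAE grade 5 is death. A definition that names grades 3 and 4 and stops there leaves out the most severe outcome. Most fatal toxicities would first be recorded at grade 3 or 4 and so would count. The exception is a sudden related death with nothing graded 3 or 4 before it in the window.

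The protocol itself names hazards that could act this way: seizures at higher enzalutamide concentrations (Section 1.5), possible QTc prolongation (Section 7.2), and hypokalemia that calls for cardiac monitoring at grades 3 and 4 (Section 9.6). In phase I the on-study EKG falls on day 57, the last day of the DLT window, so a QTc problem before then could have no graded record.

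At stake are the step from 300 mg to 600 mg and the dose then given to the 42 patients in the phase II combination arm.

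**Working it through.** **The plan's threshold.** 4/12 = 33.3% and 3/12 = 25.0%. The rule therefore passes a 12-patient cohort with at most 3 DLTs and fails it at 4.

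**Does any readable text bring a death into the count?**

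| Section | Content | Adds grade 5 to the DLT count? |
|---|---|---|
| 5.2 | Grades 3 and 4, related, day 29–57 | No |
| 5.1.1.1 | Uses the DLT count; does not redefine it | No |
| 9.3, 9.7 | Open-ended wording from grade 3 upward, for holding or reducing drug in one patient | No |
| 10.5 | How a death is reported | No |
| 10.8.5 | Monitor reviews deaths and may stop the study | No |

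**Boundary case.** Three patients with grade 3–4 DLTs and a fourth who dies suddenly of a related cause, among 12: counted as written, 3/12 = 25.0%, pass. Counted with grade 5, 4/12 = 33.3%, fail.

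**Chance that the result changes, given one such death.** The other 11 patients must contribute exactly 3 DLTs. With 2 or fewer the cohort passes under either count; with 4 or more it fails under either. If p is the chance that a patient has a grade 3–4 DLT, and patients are independent:

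P = C(11,3) p³ (1−p)⁸, with C(11,3) = 165

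- p = 0.10: 165 × 0.001 × 0.4305 = 0.071
- p = 0.20: 165 × 0.008 × 0.1678 = 0.221
- p = 0.25: 165 × 0.015625 × 0.1001 = 0.258
- p = 0.30: 165 × 0.027 × 0.05765 = 0.257

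**Unconditional chance.** Let q be the chance that a patient has a related death with no grade 3–4 record. The chance that a 12-patient cohort passes as written but fails with grade 5 counted is

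P(at most 3 of 12 at rate p) − P(at most 3 of 12 at rate p + q)

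For example, with p = 0.20 and q = 0.01: 0.7946 − 0.7674 = 0.027.

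| p | q = 0.1% | q = 0.5% | q = 1% |
|---|---|---|---|
| 0.10 | 0.1% | 0.4% | 0.9% |
| 0.20 | 0.3% | 1.3% | 2.7% |
| 0.30 | 0.3% | 1.5% | 3.1% |

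All values of p and q are assumptions. The documents give neither a DLT rate nor a related-death rate for the combination. Values of q between 2% and 5% would give differences of about 6 to 16 percentage points for p between 0.20 and 0.33, but nothing in the documents supports a q that high.

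The decision rules for 6-patient cohorts are in Figure 3, which is not shown, so the effect on the step from 300 mg to 600 mg cannot be calculated.

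**The case against.** The best reply is that nobody would apply the wording literally. Section 9.3 uses the closed and the open-ended grade ranges for the same action, holding drug, so the authors seem to treat them as interchangeable. A related death would be reported promptly (Section 10.6), discussed at weekly safety meetings and weekly phase I teleconferences (Section 10.8.4), and reviewed by a monitor who can stop the trial. Section 5.2 also speaks of examining safety before escalation, which is broader than a tally. The uncounted case needs several things at once: a death inside 28 days, judged potentially related, with no graded precursor, in a cohort already at the boundary. The background sections describe both drugs as generally well tolerated. Finally, Figure 3 is not visible and might say something about deaths.

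Most of this stands as an argument about likelihood. The wording is very probably a slip, and unexamined escalation after a death is unlikely. But each safeguard is a reporting duty or a discretionary power, and none says that the death is a DLT. Section 5.1.1.1 presents Figure 3 as illustrating the dose rules, and no visible text says that it defines DLT. A fixed threshold of 4 in 12 should not rely on readers to correct its numerator.

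**Conclusion.** The point holds: as worded, the rule is wrong, though its practical weight is low. The DLT definition omits grade 5, and the readable text does not restore it. The consequence is confined to related deaths in the window without an earlier grade 3–4 record. One such death changes the 12-patient result with probability 7% to 26% over assumed DLT rates of 10% to 30%. Before any death has occurred, the chance is at most about 3% if such deaths have an assumed rate of 1% or less. These figures assume independent patients and a full cohort of 12. The conclusion about the wording needs none of these assumptions; it depends only on Figure 3 containing no rule on deaths, which cannot be checked here.

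**What to change.** In Section 5.2, define a DLT as a toxicity of grade 3 or higher, including grade 5 (related death), that is potentially related to therapy. The 4-in-12 threshold stays as it is, and Section 9.3 needs no change because it concerns dosing of individual patients. If Figure 3 states a grade range, it should match.

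The cost is a few words, with no effect on sample size, visits or data collection.

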5.3 Phase II Study Drug Administration (Figure 4)

- Eligible subjects will be enrolled and registered within the first 12 weeks of standard of care enzalutamide 160mg/day for CRPC and randomized to one of the following two arms:
 - Arm 1: Enzalutamide 160mg/day standard dose
 - Arm 2: Enzalutamide + Mifepristone at RP2D
- Subjects will begin randomized study treatment after 12 weeks of standard of care enzalutamide lead-in. Treatment on study may start up to 14 weeks after initial enzalutamide (+2 week grace period).

Figure 4: Phase II Enrollment and Study Treatment timeline

6.0 DURATION OF TREATMENT

Therapy with enzalutamide or enzalutamide/mifepristone will continue until one of the following events occurs.

1. Progression of disease according to 2008 PSAWG-2 criteria⁴⁷ is met (Appendix C, D). Note-PSA progression (or response) will not be assessed until the patients' first 12-week disease assessment visit.
2. Unacceptable toxicity is encountered.
3. Patient withdraws consent
4. Patient is withdrawn from study at the discretion of the investigator

7.0 STUDY ASSESSMENTS

These assessments are summarized in the study calendar below.

7.1 Pre-treatment Screening Evaluation

Eligible patients who have signed informed consent and have had eligibility confirmed will be seen in the outpatient clinic within two weeks of starting the study. They will undergo a history and physical examination, have ECOG performance status, concomitant medications, and baseline toxicity documented at this visit. In addition, to confirm eligibility, the patient will have standard of care screening labs drawn within four weeks of initiating therapy. These include: CBC (white blood cell count, hemoglobin, platelet count, white blood cell differential) and serum chemistries (sodium, potassium, chloride, bicarbonate, blood urea nitrogen, creatinine, glucose, calcium, alanine aminotransferase, aspartate aminotransferase, total bilirubin, total protein, alkaline phosphatase, and albumin), LDH, serum testosterone and

PSA. A whole blood sample for circulating tumor cell correlative study will be performed during the screening period and processed as described in Section 12.1. An optional pre-study tumor biopsy will be obtained during screening period (see section 12.2). Subjects will have an EKG to insure normal QTc prior to enrolling.

Disease burden evaluation with a nuclear medicine bone scan (or Fluoride PET), abdominal/pelvis imaging (CT or MRI), and CT chest (when clinically indicated) must be obtained within 30 days of study entry. Study entry date is defined as day of first on-study treatment as detailed in Section 5.1-5.3.

7.2 On Study Visits

On study visit will every 2 weeks through 8 weeks on study, then monthly. The frequency of visits early in the trial is to ensure adequate patient safety while on study.

For study visits, including day 1, the following full set of blood tests will need to be obtained: CBC, serum chemistries, LDH, PSA. In addition, as mifepristone can affect the hypothalamic-adrenal gland axis and to monitor for endocrine related adverse events, serum cortisol cortisol and thyrotropin will be assessed at day 1 and at the subsequent two monthly (day 29, 57) study visits. A second whole blood sample for circulating tumor cell correlative study will be performed on first day of study drug as described in Section 12.1. Other monthly assessments including ECOG status, concomitant medications etc. to be collected are outlined in the study calendar. To asses for potential QTc prolongation with the combination of study agents, a second EKG will be obtained after both medications at steady state. Note: monthly visits can occur ± 3 days of scheduled visit.

Disease assessment with imaging (as in pre-study evaluation) will be repeated every 12 weeks while on study, starting at first day of concomitant daily study drug administration.

7.2.1 Pharmacokinetics sampling:

Plasma samples to determine enzalutamide and M2 metabolite levels within the serum of patients on study will be collected and sent to Medivation Inc. for pharmacokinetic (PK) analysis. Patients should withhold enzalutamide administration prior to visits with PK sampling and should take enzalutamide after the PK sample is collected. The pre-dose PK sample should be taken immediately before enzalutamide administration. The PK sample should be collected even if patient did not withhold enzalutamide.

For the phase I study, the following samples will be collected for PK modeling before enzalutamide, mifepristone dose for each day. Samples will be taken weekly starting at day 29 for the next four weeks.

1. Day 29
2. Day 36
3. Day 43
4. Day 50
5. Day 57 (4 weeks after start of phase I daily concomitant dosing)

For patients in the Phase II portion of the study, PK's will be collected on day 1 of on-study period (steady-state enzalutamide alone) and after 4 weeks on study.

All samples will be shipped to:

[name], Sample Receiving
inVention Health Clinical Lab, Inc.
[name]
[name]
[contact]
[contact]
Email: [contact]

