8.0 STUDY CALENDAR

	Screening ^m	Day1, 15, 29, 43, 57 then Monthly ^g	Every 3Months ^g (beginning at start of concomitant dosing)	Offstudy visit ^j
Procedures				
Informed Consent ^a	X			
Medical History, including demographics	X			
Physical exam, including height (only at screening) and weight	X	X	X	X
Vital Signs ^b	X	X	X	X
ECOG performance status	X	X	X	X
Concomitant medications	X	X	X	X
Adverse Events		X	X	X
EKG	X	X ⁱ		
Laboratory Assessments				
CBC with platelets & Differential counts	X	X	X	X
Serum chemistry and electrolytes ^c	X	X	X	X
LDH	X	X	X	X
PSA	X	X	X	X
Testosterone	X		X	X
Hypothalamic-pituitary labs		X ^k		
PK sample-per Sec. 7.2.1		X ^h		
TumorAssessments^d				
Bonescan/F18 PET ^e	X		X	X
CT or MRI of the abdomen/pelvis	X		X	X
CT chest ^f	X		X	X
Correlative Studies				
Circulating tumor cell (CTC) collection	X	X ⁱ		X
Tumor biopsies (optional)	X			X

- a. Written informed consent must be obtained before any study-specific screening assessments are performed (it can be no more than 28 days prior to starting/beginning study medication).
- b. Includes blood pressure, pulse, respiratory rate, and body temperature.
- c. Serum chemistry includes BUN, creatinine, ALT, AST, glucose, alkaline phosphatase, total bilirubin, electrolytes (K+, Cl-, Na+, CO2, Ca+).
- d. Imaging will be evaluated at screening and for clinical benefit every 12 weeks (3 cycles) of treatment, beginning at start of concomitant drug dosing (day 29 for phase I, day 1 for phase II).
- e. Isolated new lesions on bone scan at the first 12-week scan will be confirmed with a repeat bone scan at 6 weeks to rule out bone scan flair.
- f. Obtain if clinically warranted.
- g. +/- 3 days.
- h. PK assessments per Section 7.2.1(day 29, 43, 57 then monthly)
- i. Whole blood for CTC assessment will be collected on Day 1 of study drug administration.
- j. End of study visit – within 30 days of the last enzalutamide dose. Tumor assessment not necessary if done within preceding 30 days.
- k. Serum TSH and AM cortisol will be measured at day 1, 29, 57

1. EKG to assess QTcon study will be obtained Day 57 for Phase I, Day 29 for Phase II

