size of 84 patients (42/arm) is required, using a one-sided test at the $\alpha=0.10$ significance level. This assumes a two-year accrual period and a subsequent one-year follow-up period. Kaplan-Meier⁴¹ curves will be generated and the two treatment arms compared using a logrank test. Median time to event in each group will be estimated along with 90% confidence intervals using the method of Brookmeyer and Crowley⁴². Cox⁴³ proportional hazards regression models will be fit to assess and adjust for the effects of baseline covariates. Overall survival and radiographic progression-free survival will be analyzed similarly. The relative PSA change within each arm will also be reported using a waterfall plot according to working group recommendations for phase II studies in CRPC, as a secondary endpoint⁴⁴. Adverse events will be summarized by grade and type and compared between groups using chi-square or Fisher's exact tests.

For the secondary endocrine PD endpoint, we will compare endocrine PD marker differences between the enzalutamide alone versus the Enzalutamide + Mif treatment arms. In previous placebo controlled trials of Mif, serum cortisol levels reliably doubled from a baseline of approximately 15 $\mu\text{g}/\text{dL}$ to $>30 \mu\text{g}/\text{dL}$ after treatment with mifepristone^{38,39}. Based on the reported interquartile ranges, and assuming normality of the distribution, the coefficient of variation is estimated at 50%. An interim futility analysis will be conducted after half (35) of the expected 70 PSA events are observed. At this stage we will conduct an interim analysis of the difference in cortisol levels; a lack of biomarker effect would provide justification for closing the trial. Thus, assuming a true mean for the control arm of 15 and standard deviation of 7.5 on day 29 post randomization, our sample size will provide 90% power to detect a difference of 15 vs. 22 $\mu\text{g}/\text{dL}$ between the two treatment arms, based on t-test at a two-sided alpha level of 0.05. This calculation allows for a 15% missing data rate prior to day 29 post randomization. The other endocrine laboratories collected at day 29, will be similarly compared between treatment groups.

In addition, if at the interim analysis the conditional power for the primary PSA endpoint is $<25\%$, we will consider terminating the trial for futility. This stopping rule will provide minimal power loss ($<3\%$)⁴⁴.

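### Phase II cortisol and TSH are drawn on Day 57 in both arms, but Day 29 is the only day named for any endocrine comparison; a model using both visits would add precision at almost no cost

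*Combined protocol and SAP*

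**What the plan says.** **Draws.** Section 7.2 places cortisol and TSH at three visits: "thyrotropin will be assessed at day 1 and at the subsequent two monthly (day 29, 57) study visits". Footnote k of the study calendar (Section 8.0) agrees: "Serum TSH and AM cortisol will be measured at day 1, 29, 57". Neither restricts the draws to one phase or arm. Section 7.2 also gives them a safety purpose, "to monitor for endocrine related adverse events".

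**Treatment start.** The imaging footnote of the same calendar (footnote d) fixes the clock: "beginning at start of concomitant drug dosing (day 29 for phase I, day 1 for phase II". A Phase II patient has therefore been on the assigned treatment for four weeks at Day 29 and eight weeks at Day 57.

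**Analysis.** Section 13.1 opens the endocrine comparison without naming a day: "we will compare endocrine PD marker differences between the enzalutamide alone versus the Enzalutamide + Mif treatment arms". The power calculation is then set at Day 29, "assuming a true mean for the control arm of 15 and standard deviation of 7.5 on day 29 post randomization", and claims that "our sample size will provide 90% power to detect a difference of 15 vs. 22" µg/dL by a two-sided 5% t-test, allowing for 15% missing data before Day 29. TSH falls under the next sentence: "The other endocrine laboratories collected at day 29, will be similarly compared between treatment groups". Section 13.1 also adds an interim look at cortisol when half of the 70 PSA events have occurred. No day is named for that look, and absence of a biomarker effect there may justify closing the trial. Section 13.3 adds no endocrine analysis.

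**The concern.** A second on-treatment measurement is collected in both randomised arms but has no place in the statistical plan. The endocrine effect is the first secondary objective (Section 2.2), and the cortisol result can contribute to stopping the trial, so its precision matters most at the interim, when fewest patients are available. Without a Day 57 comparison, the plan also does not examine whether the effect lasts beyond four weeks. The samples are already scheduled, so using them needs no extra visit or patient.

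**Working it through.** **1. Inputs.** From Section 13.1: difference 22 − 15 = 7 µg/dL; control SD 7.5; coefficient of variation (CV) 50%; two-sided alpha 0.05; 42 per arm; 15% missing, so 42 × 0.85 = 35.7, taken as 35 per arm. The documents state no SD for the treated arm. I use 7.5 in both arms, and as an alternative 0.50 × 22 = 11 in the treated arm. The correlation rho between a patient's Day 29 and Day 57 values is not given; I assume 0.5, 0.7 and 0.9.

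**2. The plan's own figure.** Power comes from the noncentral t distribution with noncentrality 7/SE, where SE = sqrt((SD1² + SD2²)/n).
- SD 7.5 in both arms, n = 35: SE = sqrt(112.5/35) = 1.79; power 97%. The stated 90% is therefore conservative for the full sample.
- With these inputs 90% needs about 25 evaluable per arm, close to the interim size in step 4.
- SD 7.5 and 11, n = 35: SE = sqrt((56.25 + 121)/35) = 2.25; power 87%.

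**3. Using both visits, with equal effect and SD on each day.** The variance of a two-visit mean is SD² × (1 + rho)/2.

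| rho | Variance factor | Power, SD 7.5 in both arms | Power, SD 7.5 and 11 |
|---|---|---|---|
| Day 29 alone | 1.00 | 97.1% | 86.6% |
| 0.9 | 0.95 | 97.7% | 88.2% |
| 0.7 | 0.85 | 98.7% | 91.4% |
| 0.5 | 0.75 | 99.4% | 94.3% |

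**4. At the interim.** Assume uniform accrual of 84 patients over 24 months (3.5 a month), exponential times, and medians of 6 and 10 months (24 and 40 weeks in the plan). Expected events at month t are 1.75 × [t − (1 − exp(−λt))/λ] summed over the arms, with λ = ln 2/median. This reaches 35 at about month 19.2, or about month 17.5 if both medians are 6 months. Patients per arm past Day 29 are then 1.75 × (19.2 − 1) × 0.85 = 27 and 1.75 × (17.5 − 1) × 0.85 = 24.5, taken as 24.
- SD 7.5 in both arms: Day 29 alone 89-92%; both visits at rho 0.5, 95-97%.
- SD 7.5 and 11: 71-76% becomes 83-87% at rho 0.5.

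The gain is slightly overstated, because about 1.75 × 0.85 = 1.5 patients per arm would have reached Day 29 but not yet Day 57.

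**5. If the Day 57 effect is smaller.** Let it be smaller by a fraction r. The averaged difference is 7 × (1 − r/2). The average then loses to Day 29 alone once r exceeds about 2 × (1 − sqrt((1 + rho)/2)): 27%, 16% and 5% at rho 0.5, 0.7 and 0.9. For example, with r = 20%, rho 0.7 and SD 7.5 and 11, the averaged difference is 6.3 and power is 84.9%, against 86.6% for Day 29 alone.

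**6. Day 1 adjustment.** If Day 1 correlates with the on-treatment value at rho, the variance factor for a single visit is 1 − rho²: 0.75 at 0.5 and 0.51 at 0.7. This equals or exceeds the gain from the second visit at the same correlation.

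**The case against.** One prespecified day with a t-test is a legitimate analysis of a secondary endpoint, and on the plan's SD it already has about 97% power. Section 13.1 reports that cortisol doubled in earlier placebo-controlled trials. For 15 against 30 µg/dL with SDs of 7.5 and 15 (50% CV in each arm), power is 99.9% at 35 per arm and 98.9% at 24, so Day 57 adds almost nothing to detection. This stands, and it keeps the severity low.

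Day 57 may not measure the same effect. Section 1.8.1 reports a trough plateau at 5 to 7 days for mifepristone concentration, not for the cortisol or TSH response. By Day 57 there is more time for the drug to have been held or reduced (Section 9.3) or for hydrocortisone to have been started (Section 9.8), mostly in one arm. This also stands: step 5 shows that the average can lose power, so it should not replace the Day 29 contrast.

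Two stronger inferences are tempting. A reader might infer that the Day 57 samples serve no purpose. The documents do not support that: Section 7.2 gives them a safety use, and on the shared calendar Day 57 is the four-week combination draw for Phase I. A reader might also infer that the plan discards many patients with usable data. But the 15% allowance (42 × 0.15, about 6 per arm) is for data missing before Day 29, and patients who have left by then have no Day 57 sample. Section 13.1 does not say how many would merely miss the Day 29 visit, so few may be recovered.

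**Conclusion.** The point holds as a cheap improvement of low severity. Day 29 is the only day named for a Phase II endocrine comparison, two sentences in Section 13.1 (the general comparison and the interim look) name no day, and nothing assigns a statistical use to Day 57.

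The full-sample gain is 1 to 2 percentage points on the plan's SD, and about 2 to 8 points if the 50% CV applies to each arm's mean. At the interim with SD 7.5 it is about 5 to 7 points at correlation 0.5. These sizes rest on an assumed correlation and an equal effect and SD on both days. The treated-arm SD of 11 is inferred from the CV, and the interim numbers rest on the accrual model in step 4. The documents give no variance for TSH, so no figure is possible there.

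It would be wrong to conclude that the Day 29 comparison is underpowered or invalid: on the stated inputs it exceeds the claimed 90%.

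**What to change.** In Section 13.1:
- Analyse cortisol and TSH each with one repeated-measures mixed model using Days 29 and 57 (arm, visit, arm-by-visit), preferably adjusted for the Day 1 value.
- Keep the Day 29 arm difference as the powered contrast. Report the Day 57 difference and the two-visit average beside it.
- Name the day or days used for the interim cortisol look.

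If the sponsor prefers Day 29 alone, one sentence stating that Phase II Day 57 values are for safety monitoring only would settle the matter.

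The cost is a change of wording and slightly more analysis work, with no new samples, visits or patients. The averaged estimate can be diluted if mifepristone is held or reduced before Day 57. Keeping Day 29 as the named contrast protects the main result from that, and the separate visit estimates would show it.
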